#### Table 4 Part A study groups, interventions, and blinding

NaCI: Sodium chloride.

#### Table 5Part B study groups, interventions, and blinding

Study groups	Number of participants	Age (Min- Max years of age)	Study intervention(s adminis	Blinding	
Part B 3 µg	18	18 – 49	mRNA-CR-04 vaccine 3 µg	Intramuscular injection into the deltoid muscle, preferably of the non-dominant arm.	Observer-blind (except sponsor)
Part B 10 µg	18	18 – 49	mRNA-CR-04 vaccine 10 µg	Intramuscular injection into the deltoid muscle, preferably of the non-dominant arm.	Observer-blind (except sponsor)
Part B Placebo	6	18 – 49	Saline placebo (NaCl [0.9%])	Intramuscular injection into the deltoid muscle, preferably of the non-dominant arm	Observer-blind (except sponsor)

NaCI: Sodium chloride.

# 4.2. Scientific rationale for study design

To ensure maximum safety of the participants, as this will be the first time that the mRNA-CR-04 vaccine will be administered in humans, the study will follow an observer-blind design with staggered enrollment and dosing for Part A of the study, with study holding rules and close safety monitoring throughout the study as specified in Section 4.1 and Section 8.3.7. Part B of the study adds an even lower dose ( $3 \mu g$ ) of

mRNA-CR-04 vaccine group to allow exploration of a wider range of vaccine doses, as well as a repeat of the Part A low dose (10  $\mu$ g) of mRNA-CR-04 vaccine group, which may assist in standardizing the new 3  $\mu$ g dose group in Part B to the earlier Part A study groups.

# 4.3. Justification for dose

The proposed doses will be 3 µg, 10 µg, 30 µg, and 100 µg. The monovalent SARS-CoV-2 mRNA vaccines (Pfizer-BioNTech Comirnaty mRNA vaccine [FDA, 2023a] and Spikevax Moderna COVID-19 Vaccine [FDA, 2023b]) have been licensed in the US as a 2 or 3-dose primary series. Bivalent formulations of the Moderna and Pfizer-BioNTech COVID-19 vaccines encoding S protein sequences from Omicron BA.4/5 and the ancestral strain followed by monovalent boosters encoding XBB.1.5 since 11 September 2023, have been authorized for primary and booster vaccinations [FDA, 2023a; FDA, 2023b].

The maximum planned dose is 100  $\mu$ g. The rationale for evaluating doses from 3  $\mu$ g to 100  $\mu$ g is based on the following considerations:

- The optimal dose required to confer cross-protective immunity against non-Omicron variants, including new/emerging variants needs to be determined.
- Moderna has evaluated doses up to 250 μg (2-dose regimen) in their Phase 1 studies [Jackson, 2020].
- The doses of the authorized bivalent booster vaccines from Pfizer-BioNTech and Moderna are 30 µg and 50 µg, respectively. The initial starting dose of 10 µg of the mRNA-CR-04 vaccine in Part A of the study is well below these doses.

# 4.4. End-of-study definition

A participant is considered to have completed the study if he/she returns for the last visit as described in the protocol.

EoS: LSLV (Visit 5, Month 6) or date of the last testing released of the human biological samples, related to primary and secondary endpoints, whichever occurs later. EoS must be achieved no later than 8 months after LSLV. EoS cannot be before LSLV.

# 5. STUDY POPULATION

Adherence to the inclusion and exclusion criteria specified in the protocol is essential. Deviations from these criteria are not allowed because they can jeopardize the scientific integrity, regulatory acceptability of the study or safety of the participant.

# 5.1. Inclusion criteria

All participants must satisfy ALL the following criteria prior to dose administration:

- 1. Written or witnessed informed consent obtained from the participant prior to performance of any study-specific procedure.
- 2. Participants, who in the opinion of the investigator, can and will comply with the requirements of the protocol (e.g., completion of the eDiary and study procedures).
- 3. Has received 2 doses of primary series and booster dose(s) of an authorized or licensed mRNA COVID-19 vaccine (only Moderna or Pfizer vaccines) with the last booster dose administered at least 6 months or more prior to screening and has provided documentation of receiving the vaccination series (e.g., vaccination card).
- 4. Negative for SARS-CoV-2 infection by RT-PCR test at screening within 7 days prior to study vaccination.
- 5. Is a male or nonpregnant female of 18 to 49 years, inclusive, at screening.
- 6. If the participant is a WOCBP, the participant agrees to practice true abstinence or use at least 1 highly effective form of contraception for at least 30 days prior to study vaccination up to 1 month after study vaccination.
- 7. Agrees to refrain from blood or plasma donation from screening and up to 6 months after vaccination.
- 8. Is healthy or medically stable as determined by investigator judgment based on medical history, clinical laboratory tests, vital sign measurements, and physical examination findings.

# 5.2. Exclusion criteria

The following criteria should be checked at the time of screening and on D1 prior to dose administration. The potential participant MUST NOT be included in the study if ANY exclusion criterion applies:

# 5.2.1. Medical conditions

- Has a new onset, clinically significant, abnormal biochemistry or hematology finding (defined as ≥Grade 1) at screening (participants with Grade 1 laboratory abnormalities that have been stable for at least 6 months before enrollment may be included in the study).
- 2. Has any medical disease or condition that, in the opinion of the investigator, precludes study participation. This includes any acute, subacute, intermittent, or chronic medical disease or condition that would place the participant at an unacceptable risk of injury, render the participant unable to meet the requirements of the protocol, or may interfere with the evaluation of responses or the participant's successful completion of the trial.
- 3. Any confirmed or suspected immunosuppressive or immunodeficient condition, based on medical history and physical examination (no laboratory testing required).

- 4. History of myocarditis, pericarditis, second and third degree heart block or idiopathic cardiomyopathy, or presence of any medical condition that increases risk of myocarditis or pericarditis, including cocaine abuse, cardiomyopathy, endomyocardial fibrosis, hypereosinophilic syndrome, hypersensitivity myocarditis eosinophilic granulomatosis with polyangiitis, persistent myocardial viral infection (e.g., due to enterovirus or adenovirus).
- 5. Has an acute febrile illness with a temperature ≥38.0°C or ≥100.4°F observed by the participant or at the study site within 72 hours prior to study vaccination. Participants with suspected COVID-19 symptoms (Section 8.4.4.2.2) should be excluded and referred for medical care.
- 6. Has a history of hypersensitivity or severe allergic reaction, including anaphylaxis, generalized urticaria, angioedema, and other significant reactions to any previous vaccine, or any component of the study vaccine.
- 7. Has a body mass index  $>40 \text{ kg/m}^2$ .
- 8. Has had known close contact with anyone who had a confirmed SARS-CoV-2 infection within 14 days before study vaccination.
- 9. Has a history of documented SARS-CoV-2 infection or COVID-19 within 6 months before the date of screening visit.
- 10. Has any self-reported or medically documented clinically significant medical or psychiatric condition. Significant medical conditions include, but are not limited to, the following:
  - a. Moderate or severe respiratory disease (e.g., chronic obstructive pulmonary disease, asthma).
  - b. Uncontrolled hypertension, defined as an average systolic blood pressure ≥140 mmHg or an average diastolic blood pressure ≥90 mmHg, based on an average of up to 3 blood pressure measurements.
  - c. Clinically significant cardiovascular disease (e.g., congestive heart failure, cardiomyopathy, ischemic heart disease).
  - d. Neurological or neurodevelopmental conditions (e.g., Down syndrome, dementia, chronic migraine not controlled by medication, epilepsy, stroke or seizures in the last 3 years, encephalopathy, focal neurologic deficits, Guillain-Barré syndrome, encephalomyelitis, or transverse myelitis).
  - e. Ongoing malignancy or recent diagnosis of malignancy in the last 5 years (excluding basal cell and squamous cell carcinoma of the skin).
  - f. Tuberculosis or non-tuberculosis mycobacterial infection.
  - g. Autoimmune disease, including hypothyroidism without a defined nonautoimmune cause.
  - h. Immunodeficiency of any cause, including from solid organ transplant, blood, or bone marrow transplant, or use of other immune-weakening medicine.
  - i. Type 1 or 2 diabetes mellitus regardless of disease control.
- 11. Has any of the following self-reported or medically documented risk factors for severe COVID-19:

- a. Chronic kidney disease
- b. Cerebrovascular disease
- c. Cystic fibrosis
- d. Chronic liver disease
- e. Pulmonary fibrosis

## 5.2.2. Prior/concomitant therapy

- 12. Has participated or plans to participate in another investigational study involving any investigational drug or device within 60 days or 5 half-lives, whichever is longer, before study vaccination and throughout the study.
- 13. Has received a licensed or authorized non-mRNA COVID-19 vaccine (primary series or booster dose).
- 14. Has received or plans to receive any licensed vaccine within 4 weeks before or after study vaccination. Inactivated vaccines for influenza are permitted during the study if they are administered at least 14 days before or after study vaccination.
- 15. Is planning to receive an authorized or licensed COVID-19 booster vaccination for the duration of the study (for participants who are not covered by local recommendations to receive booster per current standard of care) OR is planning to receive an authorized or licensed COVID-19 booster vaccination on or before Day 31 of the study (for participants covered by local recommendations to receive booster).
- 16. Has received or plans to receive immunoglobulins or any blood or blood products within 90 days before study vaccination and throughout the study.
- 17. Reports chronic use (more than 14 continuous days) of any medication that may be associated with changes in immune function including, but not limited to, systemic corticosteroids exceeding 20 mg/day of prednisone equivalent, allergy injections, immunoglobulins, interferons, immunomodulators, cytotoxic drugs, or other similar or toxic drugs within 6 months of study vaccination. Note: The use of low-dose topical, ophthalmic, inhaled, intra-articular and intranasal steroid preparations is permitted.

## 5.2.3. Other exclusions

- 18. Pregnant or lactating female.
- 19. Female participant planning to become pregnant or planning to discontinue contraceptive precautions within 1 month following study vaccination.
- 20. Participant is an employee or family member of the investigator or study site personnel.

## 5.3. Screen failures

A screen failure is an individual who consents to participate in this study but is not entered in the study/assigned to a study intervention.

Limited data for screening failures (including informed consent, inclusion/exclusion criteria, demographic data, pregnancy reason for screening failure and any SAEs that occurred at the visit) will be collected and reported in the eCRF.

If the investigator believes there is a reasonable justification to do so, all screening procedures may be repeated (maximum 1 re-screening per participant is allowed) under a new participant number. The participant can only be randomized into the study once the investigator receives the results and confirms the eligibility criteria.

Participants with hematological/biochemical values out of normal range which are expected to be temporary may be re-screened at a later date, as per the above conditions.

# 5.4. Criteria for temporarily delaying enrollment, randomization and study intervention administration

Enrollment, randomization and study intervention administration may be postponed within the 14-day screening interval until transient conditions cited below are resolved:

- Acute disease and/or fever at the time of enrollment and/or study intervention administration. Refer to the Section 1.3 for definition of fever and oral temperature in this study.
- Participants with a minor illness (such as mild diarrhea, mild upper respiratory infection) without fever may be enrolled and/or dosed at the discretion of the investigator.
- If antipyretics and/or analgesics and/or antibiotics have been used within 3 days prior to study intervention administration.

# 6. STUDY INTERVENTION AND CONCOMITANT THERAPY

Refer to the Definition of terms for the definition of study intervention.

# 6.1. Study interventions administered

Refer to Section 1.2 for the study intervention administration schedule. Table 6 and Table 7 describe study interventions to be administered for Part A and Part B, respectively.

#### Table 6 Part A study interventions administered

	mRNA-CR-04		Placebo
Study intervention#: Group 1	COV08A/DL001Z		PL001Z
Group 2	COV08B/DL001Z		PL001Z
Group 3	COV08C	PL001Z	
Study intervention formulation#: Group 1	GSKVx000000037755 (Dose Aa GSKVx00000037754); Excipients; Water for injections	Excipients; Water for injections	
Group 2	GSKVx000000037755 (Dose Ab GSKVx000000037754); Excipients; Water for Excipients; Water for injections injections		Excipients; Water for injections
Group 3	GSKVx00000037755 (Dose Ac GSKVx00000037754); injections	Excipients; Water for injections	
Presentation: Group 1	Concentrate for dispersion for injection (vial)	Solution for dispersion for injection (vial)	Solution for injection (vial)
Group 2	Concentrate for dispersion for injection (vial)	Concentrate for dispersion for injection (vial) Solution for dispersion for injection (vial)	
Group 3	Dispersion for injection (vial)		Solution for injection (vial)
Туре:	Investigational	Placebo	
Product category:	Biologic		Drug
Route of administration:	IM		IM
Location	Deltoid	Deltoid	
Directionality	NA	NA	
Laterality*	Non-Dominant	Non-Dominant	
Number of doses to be administered	1		
Volume to be administered by dose **	0.3 mL	0.3 mL	
Packaging and labeling:	Refer to the PM for more details		Refer to the PM for more details
Manufacturer:	GSK		Hospira

Ab: Antibody; IM: Intramuscular; GSK: GlaxoSmithKline Biologicals SA; NA: Not applicable; PM: Pharmacy manual.

\*The non-dominant arm is the preferred arm of injection. In case it is not possible to administer the study intervention in the non-dominant arm, an injection in the dominant arm may be performed.

\*\*Refer to the PM for the volume after reconstitution.

\*Coding serves for internal sponsor anonymization

#### Table 7 Part B study interventions administered

		Placebo				
Study Groups	Part B 3 µg		Part B 10 µg	Part B Placebo		
Study intervention #	COV08D/DL001Z		COV08A/DL001Z	PL001Z		
Study intervention formulation # :	GSKVx000000037755 (Dose Ad GSKVx000000037754); Excipients; Water for injections Water sor injections		GSKVx00000037755 (Dose Aa GSKVx00000037754); Excipients; Water for injections	Excipients; Water for injections	Excipients; Water for injections	
Presentation:	Concentrate for dispersion for injection (vial) Solution for dispersion for injection (vial)		Concentrate for dispersion for injection (vial)	Solution for dispersion for injection (vial)	Solution for injection (vial)	
Туре:	Investigational	Investigational		Placebo		
Product category:		Biologic			Drug	
Route of administration:			Μ		IM	
Location		Del	Itoid		Deltoid	
Directionality		N	IA		NA	
Laterality*		Non-Do	ominant		Non-Dominant	
Number of doses to be administered	1				1	
Volume to be administered by dose **	0.3 mL				0.3 mL	
Packaging and labeling:		Refer to the PM for more details				
Manufacturer:		G	SK		Hospira	

Ab: Antibody; IM: Intramuscular; GSK: GlaxoSmithKline Biologicals SA; NA: Not applicable; PM: Pharmacy manual.

\*The non-dominant arm is the preferred arm of injection. In case it is not possible to administer the study intervention in the non-dominant arm, an injection in the dominant arm may be performed.

\*\*Refer to the PM for the volume after reconstitution.

#Coding serves for internal sponsor anonymization

# 6.2. Preparation, handling, storage, and accountability

The study interventions must be stored in a secured place within the temperature range specified on the study intervention's label. The storage temperature should be continuously monitored and recorded with a calibrated (if not validated) temperature monitoring device.

Only unblinded staff should be allowed access to the study interventions. Storage conditions will be assessed by a sponsor study contact during pre-study activities. Refer to the PM for more details on storage and handling of the study interventions.

# 6.3. Measures to minimize bias: randomization and blinding

This is a dose-escalation, observer-blind, randomized study.

## 6.3.1. Participant identification

Participant identification numbers will be assigned sequentially to the individuals who have consented to participate in the study by using an automated internet-based system (e.g., IRT).

## 6.3.2. Randomization to study intervention

The randomization of study interventions will be performed using the IRT system.

#### 6.3.3. Intervention allocation to the participant

In Part A of the study, approximately 72 participants will be enrolled with 24 participants per group. These 24 eligible participants will be randomly assigned to investigational mRNA-CR-04 vaccine or saline placebo in a (3:1) ratio. In Part B of the study, approximately 42 participants will be enrolled and randomly assigned to 3  $\mu$ g investigational mRNA-CR-04 vaccine, 10  $\mu$ g investigational mRNA-CR-04 vaccine, or saline placebo in a (3:3:1) ratio.

## 6.3.4. Blinding and unblinding

In Part A of the study, data will be collected in an observer-blind manner. The participant, the site and sponsor personnel involved in the clinical evaluation of the participants are blinded while other study personnel may be aware of the treatment assignment. To do so, study interventions will be prepared and administered by qualified study personnel who will not participate in data collection, evaluation, review, or the entry of any study endpoint data (i.e., reactogenicity, safety, immunogenicity). In Part B of the study (i.e., following the Part A Day 15 interim analysis), continuation of the observer-blind design will be restricted to study participants and site personnel involved in the clinical evaluation of the participants, while sponsor personnel will no longer remain blinded to treatment assignment.

Unblinding a participant's individual study randomization number should occur ONLY in case of a medical emergency when this information is essential for the clinical management or welfare of the participant.

In case of emergency, the investigator can have unrestricted, immediate and direct access to the participant's study intervention information via the IRT. The investigator may contact Signant Health support (refer to Table 8) if help is needed to access participant's study intervention information (i.e., if the investigator is unable to access IRT).

A physician other than the investigator (e.g., an emergency room physician) or participant may also request emergency access to the participant's study intervention information via the investigator.

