# **PROTOCOL AMENDMENT 3 SUMMARY OF CHANGES TABLE**

#### Document Date Substantial Region 07 Feb 2024 United States (US) Amendment 3 Yes 15 Nov 2023 Amendment 2 United States (US) Yes Amendment 1 03 Oct 2023 Yes United States (US) Original Protocol 11 May 2023 \_ -

### DOCUMENT HISTORY

### **Overall Rationale for the Amendment:**

The Protocol Amendment 3 has been amended to allow for additional Day 31 interim analyses and to add a Part B to the study following the Day 15 interim analysis, during which a lower dose  $(3 \mu g)$  of the mRNA-CR-04 vaccine will be evaluated and sponsor personnel will be unblinded.

Section # and Name	Description of Change	Brief Rationale
Section 1.1 (Synopsis), Section 1.2 (Schema), Section 4.1 (Overall design), Section 4.2 (Scientific rationale for study design), Section 4.3 (Justification for dose), and Section 6.3.3 (Intervention allocation to the participant).	This study is divided into two parts (Parts A and B). Part B will commence only after all Part A participants have completed their Day 15 study visits and the Day 15 interim analysis is completed. In Part B, 42 more participants will be enrolled in parallel and randomly assigned in a 3:3:1 ratio to receive: (a) 3 µg mRNA-CR-04 vaccine, or (b) 10 µg mRNA-CR-04 vaccine, or (c) saline placebo.	To explore a wider range of vaccine doses and to repeat the 10 µg dose vaccine group, which may assist in standardizing the Part B to Part A study groups.
Section 1.1 (Synopsis), Section 1.2 (Schema), Section 4.1 (Overall design), Section 6.3.4 (Blinding and unblinding), Section 8.3.7.1 (Staggered administration of study intervention), Section 8.3.7.4 (SRT and iSRC evaluation), and Section 8.4.4.2.1 (Myocarditis and pericarditis: definitions and assessment).	Text modified to allow unblinding of sponsor personnel (including the SRT) to individual level treatment assignments following the Part A Day 15 interim analysis. The observer-blind will be maintained at the site level.	Practical consideration to allow all sponsor personnel to use unblinded data analyses from this initial phase 1 trial to plan further clinical development of the investigational vaccine platform. The SRT will no longer need to rely on the iSRC as the sole reviewer of unblinded safety data.

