#### 8.2.2. Laboratory assays

Following laboratory assays will be performed (Table 10).

- PCR assay will be used to detect SARS-CoV-2 infection. If the sample is positive and sufficient material is available, sequencing of the SARS-CoV-2 isolate will be performed by genomic RNASeq.
- Serological assay to monitor the asymptomatic infection will be performed using an ECL to measure serum-binding Abs IgG levels specific for N protein of SARS-CoV-2.
- The vaccine-induced humoral immunity will be evaluated using serological assays determining the capacity of the serum of SARS-CoV-2 vaccinated participants to neutralize pseudoviruses bearing S protein from vaccine encoded SARS-COV-2 and from the WT (D614G).
- Further characterization of the humoral immune response will be performed using ECL for measurement of IgG antibodies binding to the SARS-CoV-2 S protein (at least vaccine encoded SARS-CoV-2 variant and WT).
- The cell-mediated immunity will be evaluated by assessing the frequency of SARS-CoV-2 S-specific CD4+ and CD8+ T-cells expressing specific activation or immune markers using ICS per million of total CD4+ or CD8+ T-cells respectively.

Assay Type	System	Component	Challenge	Method	Laboratory**
Humoral immunity (antibody determination)*	Serum	Anti-S binding IgG Ab	ti-S binding IgG Ab		PPD
	Serum	Anti-SARS-CoV-2 neutralizing titer	NA	Pseudo Neutralization assay	Nexelis
Cell-mediated immunity	PBMCs	CD4+/CD8+ T-cells expressing IL- 2/IFNy/TNFa/IL- 13/IL-17/4- 1BB/CD40L	Peptide pools covering the SARS-CoV-2 S protein	ICS	GSK
Detection of SARS- CoV-2 Infection	Serum	Anti-N IgG Ab	NA	ECL	PPD
Detection of SARS- CoV-2 Infection	Nasopharyngeal Swab	SARS-CoV-2 RNA	NA	RT-PCR	PPD
Sequencing of SARS-CoV-2 Isolates	Nasopharyngeal Swab	SARS-CoV-2 RNA	NA	RNASeq	PPD

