#### Table 10Laboratory assays

Ab: Antibody; CD40L: Cluster of differentiation 40 ligand; 4-1BB: CD137 (tumor necrosis factor receptor superfamily 9); CRO: Contract research organization; ECL: Electro-chemiluminescence assay; GSK: GlaxoSmithKline Biologicals SA; ICS: Intracellular cytokine staining; IgG: Immunoglobulin G; IFNγ: Interferon gamma; IL-2: Interleukin-2; IL-13: Interleukin-13; IL-17: Interleukin-17; NA: Not applicable; N: Nucleocapsid; PPD: Pharmaceutical Product Development; RNASeq: RNA Sequencing; RT-PCR: Real-time polymerase chain reaction; S: Spike; TNFα: Tumor necrosis factor alpha; WT: Wild type.

\* Measurement of humoral immunity against vaccine encoded SARS-CoV-2 and WT strains.

\*\* Refer to the list of clinical laboratories for details.

Please refer to Section 10.2 for further details.

The addresses of clinical laboratories used for sample analysis are provided in a separate document accompanying this study protocol.

GSK clinical laboratories have established a quality system supported by procedures. The activities of GSK clinical laboratories are audited regularly for quality assessment by an internal (sponsor-dependent) but laboratory-independent quality department.

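### The plan unblinds sponsor personnel after the Part A Day 15 interim with no exception for the sponsor's own laboratory, which runs the T-cell (ICS) assay

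*Protocol*

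**What the plan says.** **Who runs the assay.** Table 10 (Protocol 8.2.2) places binding IgG, anti-N IgG, RT-PCR and sequencing at one outside laboratory and neutralization at another. The cell-mediated row reads "Peptide pools covering the SARS-CoV-2 S protein ICS GSK", so the sponsor is the testing laboratory. The notes to the table say that "GSK clinical laboratories have established a quality system supported by procedures" and that the laboratories are audited. They do not mention blinding.

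**Who is unblinded, and when.** Under Protocol 6.3.4, once the Part A Day 15 interim is done, the observer-blind covers only participants and the site staff who evaluate them clinically, "while sponsor personnel will no longer remain blinded to treatment assignment". Table 5 labels all three Part B groups "Observer-blind (except sponsor"). The Amendment 3 summary describes the change the same way: "Text modified to allow unblinding of sponsor personnel (including the SRT) to individual level treatment assignments following the Part A Day 15 interim analysis". It gives the reason as "Practical consideration to allow all sponsor personnel to use unblinded data analyses" in planning further development, and adds that the safety review team need no longer rely on the internal safety committee as the only unblinded reviewer.

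**What the SAP adds.** SAP 4.8.1 gives a restricted sponsor team access to unblinded individual data at the Day 15 interim, and unblinds the sponsor's statistical team to individual participants for later analyses. It is silent on all other sponsor staff.

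**The concern.** Whoever turns a blood sample into an endpoint value should not know the arm. For ICS that person works for the sponsor, and the sponsor as a whole is released from the blind. If the rule is followed as written, nothing stops the people who run, read, repeat or release the ICS results from knowing which samples are placebo, 3 µg or 10 µg.

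The endpoints at stake are the CD4+/CD8+ T-cell frequencies and the T-helper profiles. They are tertiary, but Protocol 2.1 rests the decision to take this construct and dose forward on safety, reactogenicity and immunogenicity together. The 3 µg dose exists only in Part B, so no 3 µg result is generated before the unblinding.

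The protocol protects other readers expressly. Section 8.3.8 has surveillance EKGs read blinded and keeps the cardiac adjudication committee blinded. No matching sentence covers the ICS laboratory.

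**Working it through.** The plan states no figure on this point, so the check has two parts: the wording side by side, and a count of the samples affected.

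**Wording**

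| Question | Protocol | SAP |
|---|---|---|
| Who runs ICS? | The sponsor (Table 10) | Laboratory not named (4.4.2) |
| Who stays blinded after the interim? | Participants and site clinical staff only (6.3.4) | Investigators and participants (4.8.1) |
| Who is unblinded? | Sponsor personnel, no role excepted (6.3.4, Table 5) | Statistical team named; others not addressed (4.8.1) |
| Are ICS samples coded or masked for treatment? | Not stated | Not stated |
| Must ICS results be locked before unblinding? | Not stated; the Day 15 interim lists humoral data (9.5.1) | Same (4.8.1) |

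No line of either document takes assay staff out of the unblinding.

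**Count of scheduled ICS samples**

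Inputs: 72 Part A and 42 Part B participants, all sampled (Table 11); four time points, namely Day 1, Day 15, Day 31 and Month 6 (Protocol 8.2); Part B starts only after the Part A Day 15 interim (Protocol 4.1).

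- Part A: 72 × 4 = 288
- Part B: 42 × 4 = 168
- Total: 288 + 168 = 456
- Of the Part B samples, the 3 µg group contributes 18 × 4 = 72

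The share open to unblinded reading depends on when Part A samples are assayed. The documents give no assay dates, so this is a range:

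| Assumption on Part A | Samples open to unblinded reading | Share of 456 |
|---|---|---|
| None assayed after the interim | 168 | 36.8% |
| Month 6 assayed after it | 168 + 72 = 240 | 52.6% |
| Day 31 and Month 6 assayed after it | 168 + 144 = 312 | 68.4% |
| All four time points assayed after it | 456 | 100% |

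The first row needs no assumption about Part B, because every Part B sample is drawn after the interim. The last row is possible because the immunogenicity content of the Day 15 interim is humoral, so Part A Day 1 and Day 15 ICS need not have been read by then.

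**Where the results go.** SAP 4.4.2 gives the T-cell endpoints descriptive statistics by treatment group. SAP 4.1.1 and Protocol 9.4.3 also call for combined summaries in which the groups common to both parts (10 µg and placebo) are merged. Those tables place 3 µg, read only in the unblinded period, beside 30 µg and 100 µg from Part A.

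**The case against.** The strongest reply is that permission is not access. Neither document says that treatment codes go to the ICS bench, SAP 4.8.1 names only the statistical team, and the laboratory works under procedures that are not available here and may already mask samples. The endpoint is tertiary, all analysis is descriptive, the neutralizing titer is assayed outside the sponsor, and unblinding the sponsor in Part B is a disclosed choice. All of this stands and limits the point. It does not remove it: an unseen procedure cannot be credited against a protocol rule that says the opposite, and neither stated purpose of the unblinding requires the assay bench to know the arm.

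A reader might infer more than the documents support:

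- *That Part A Day 15 ICS was read blind, giving a clean contrast with later readings.* Nothing shows this. Day 15 ICS may be read after the interim, and for Part A section 6.3.4 blinds only sponsor personnel involved in clinical evaluation, so assay staff were not clearly covered even then.
- *That the pooled model would turn a reading bias into a study-part effect.* The ANCOVA with study part as a factor is specified for neutralizing titers and binding IgG (Protocol 9.4.2.2 and 9.4.3; SAP 4.3.2.1 and 4.4.1.1). SAP 4.4.2 plans no such model for ICS.
- *That background subtraction leaves room for the analyst.* SAP 4.4.2 makes it fixed arithmetic: stimulated minus medium-only, with a floor of 1 per million cells, then a sum over peptide pools. How positive cells are identified before that step is not described.
- *That 6.3.4 already bars anyone who knows the treatment from endpoint work.* The clause "who will not participate in data collection, evaluation, review, or the entry of any study endpoint data (i.e., reactogenicity, safety, immunogenicity") applies to those who prepare and give the injection, not to everyone who knows the assignment.

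**Conclusion.** The point holds as a gap in the blinding rule, and should be closed. As written, the plan allows the sponsor's laboratory to run and read ICS samples with treatment known for at least 168 of 456 scheduled samples (36.8%), including all 72 from the 3 µg group. The number is larger to the extent that Part A samples are assayed after the interim.

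These counts assume that planned enrollment is met and every scheduled sample is taken. They measure exposure, not bias. The size of any bias cannot be estimated: the documents give no reader variability for ICS and no expected dose difference. The standard deviation in the sample-size section is for the log10 increase behind the GMR and is not stated to apply to T-cell frequencies, so it should not be borrowed for this purpose.

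The consequence is confined to the tertiary T-cell endpoints and the descriptive tables that combine the two parts. The primary safety endpoints and the secondary neutralizing titers do not depend on this assay. Whether assay staff will in fact see the assignments is not shown either way.

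**What to change.** Add one sentence to Protocol 6.3.4, with a note under Table 10. It should say that sponsor laboratory staff who run, read, review or release ICS, or any other assay performed by the sponsor, are excluded from the unblinding, and that they receive samples under codes that carry no treatment information until the results for that time point are locked. It should cover all samples from both parts, so that it does not depend on when Part A samples are assayed.

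Align SAP 4.8.1 with 6.3.4 by listing which sponsor roles are unblinded after the Part A Day 15 interim and stating that laboratory staff are not among them.

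The cost is a sentence in each document and an access restriction. It needs no extra samples, visits or staff. The safety review team's unblinded review, the statistical team's analyses and the sponsor's development planning can go ahead as intended. If the laboratory already works from masked samples, the change only records that practice.
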